#### 5.5.7.4. PPV for Changes in Planned Treatment

PPV will be calculated from imaging and histology results for the subset of subjects who had a change in the planned protocol procedure. Only a subset of these subjects may have tissue available for PPV.

Criteria for Positive PyL Imaging Result	Criteria for Procedure and Positive Histology
--	--

If subject in Cohort A and category=PYL and Is the 18F-DCFPyL PET/CT scan consistent with PSMA Positive cancer uptake = yes and Location of lesion count from imaging = location of lesion from histology and Lesion count for location >=1 from imaging	If Cohort A and prostatectomy and lymphadenectomy performed=no and Reason= Other, unscheduled Biopsy='Yes' and Pathology result=Positive for prostate cancer
If Cohort B and category = PYL and Prostate gland right lesion count $\geq 1$ or Prostate gland left lesion count $\geq 1$	If Cohort B and Biopsy performed =no and Adenocarcinoma present at right or left side of prostate = yes
If Cohort B and category = PYL and positive imaging criteria from Section 5.5.7.1 is met.	If cohort B and biopsy performed = no and ≥1 positive lymph node on right or left template, pre-sacral nodes, or other pelvic lymph nodes

The denominator of the above subset is the subset of subjects who had a change in the planned protocol procedure defined in Figure 1 and who had both imaging and histology results.

If imaging results are not evaluable then this endpoint is missing.

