10.3. Prostatectomy and Lymphadenectomy

Within 28 days post-study drug injection, all subjects in Cohort A will undergo standard of care RP with PLND as detailed in the Surgical Manual. Extent of PLND will be captured in the eCRF.

Surgical staff will label all specimens removed during surgery to correlate with the specific anatomic location of removal, in accordance with the Surgical Manual.

Should a subject receive alternate or additional procedure(s) for prostate cancer after dosing, the procedure and corresponding histopathology data will be recorded in the eCRF.

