12.5.2.3. Exploratory Analyses

Analyses will be generated on the evaluable set for the following exploratory endpoints:

- The number of lesions per subject will be plotted against baseline PSA and baseline testosterone for each of the three central imaging core lab independent readers using evaluable subjects from both cohorts.
- SUV_{max}, SUV_{peak} and SUVr will be summarized for each tissue type (e.g., bone, lymph nodes, soft tissue, and prostate gland) and each of the three central imaging core lab independent readers using evaluable subjects from both cohorts. The relationship between SUVr in prostatic lesions and baseline PSA and testosterone levels, and Gleason score at time of radical prostatectomy will be evaluated.
- Sensitivity, SUV_{max}, SUV_{peak}, and SUV_r will be computed for the following subgroups in Cohort A:
 - Previous radiation therapy (yes/no)
 - Previous hormonal therapy (yes/no)
 - Previous chemotherapy (yes/no)
- SUV_{max}, SUV_{peak}, and SUV_r will be summarized with positive and negative histopathology. Each will be summarized by Gleason score for the single or dominant prostate tumor nodule.
- The clinical management plans before and after review of ¹⁸F-DCFPyL PET/CT scans will be summarized.

An exploratory analysis of PPV of ¹⁸F-DCFPyL PET/CT imaging in subjects who are excluded from the *evaluable set* but have corresponding histopathology outside the planned protocol procedure will be performed on the *safety set*.

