## 3.1.3. Exploratory Objectives

- 1. To assess F-DCFPyL uptake among lesion locations (e.g., bone, lymph nodes, soft tissue, prostate gland)
- 2. To assess the relationship between F-DCFPyL uptake in prostatic and extra-prostatic lesions with baseline PSA and testosterone levels and Gleason Score at time of radical prostatectomy
- 3. To assess the diagnostic performance of F-DCFPyL PET/CT imaging to detect prostate cancer within the prostate gland (Cohort A)
- 4. To assess the impact of F-DCFPyL PET/CT imaging on clinical management plan
- 5. To determine PPV of F-DCFPyL PET/CT imaging for lesions detected by PET that are outside the planned surgical template or biopsy site

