#### 5.4.4. Change in Planned Protocol Procedure Set

The change in planned protocol procedure set includes dosed subjects in Cohort A who did not have a prostatectomy and lymphadenectomy due to change of planned management, and subjects in Cohort B who did not have conventional guided biopsy due to change of planned management. See figure 1 above for definition of change in planned management.

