- Clinical management questions pre- and post F-DCFPyL PET/CT imaging will be summarized from the questionnaire evaluated by a central reader. The proportion of subjects in Cohort A who had a change in intended clinical management plan from pre-to post PyL scans will be analyzed using a one sample binomial test.
- Point estimates and two-sided 95% CIs for PPV will be computed for the change of management set. An Agresti-Coull 95% confidence interval will be used will be used assuming a null hypothesis of 0.5. Results will be computed for each of the 3 central imaging core lab independent readers.

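### The Cohort A part of the changed-procedure PPV counts an unscheduled biopsy only if surgery was not done, so it is selected on a decision that may follow the biopsy result and is open to upward bias

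*SAP*

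**What the plan says.** SAP 5.5.7.4 defines positive histology for a Cohort A subject in this PPV by "If Cohort A and prostatectomy and lymphadenectomy performed=no and Reason= Other, unscheduled Biopsy='Yes" together with a pathology result positive for prostate cancer. The imaging criterion requires the PET lesion and the histology to be at the same location.

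The same section fixes the denominator: "The denominator of the above subset is the subset of subjects who had a change in the planned protocol procedure defined in Figure 1", limited to those with both imaging and histology. SAP 5.4.4 defines the Cohort A members of that set as "dosed subjects in Cohort A who did not have a prostatectomy and lymphadenectomy due to change of planned management", and SAP 4.2 likewise equates a change of plan in Cohort A with not having surgery. SAP 7.8 runs the PPV on this set, with an Agresti-Coull 95% interval that "will be used assuming a null hypothesis of 0.5".

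The objective is worded differently. SAP 3.1.3, item 5, asks for the PPV of PET/CT "imaging for lesions detected by PET that are outside the planned surgical template or biopsy site". The protocol's version of the analysis (12.5.2.3) takes subjects outside the evaluable set who "but have corresponding histopathology outside the planned protocol procedure". Protocol 10.3 has histology recorded in the eCRF in wider circumstances: "Should a subject receive alternate or additional procedure(s) for prostate cancer after dosing".

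**The concern.** Consider a Cohort A man whose PET shows a lesion outside the area to be resected and who has that lesion biopsied. If the biopsy is positive and surgery is cancelled, he enters the set as a true positive. If it is negative and the planned surgery goes ahead, the condition that surgery was not performed fails, and his false positive is not counted in this PPV.

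The nodal endpoints do not recover him. Protocol 12.3.1 leaves out PET-positive nodes in areas that were not removed, SAP 5.5.7.1 counts a positive image only where tissue was taken, and a lesion outside the pelvic nodes is beyond that endpoint altogether. His result therefore enters no planned accuracy estimate.

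At stake is the credibility of the one PPV meant to describe PET findings beyond the planned field. If the decision to operate follows the biopsy, the estimate partly reflects that decision, and comparison with 0.5 loses its meaning.

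**Working it through.** **Plan's own figure.** There is none to reproduce. Neither document states an expected PPV, a number of unscheduled biopsies or a cancellation rate for this endpoint. The Cohort A size (236 evaluable, about 262 dosed) rests on sensitivity and specificity and is not an input here.

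**Who is counted** (Cohort A, PET-positive, unscheduled biopsy at the matching location):

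| Biopsy | Surgery not done (change of plan) | Surgery done |
|---|---|---|
| Positive | true positive | not counted |
| Negative | false positive | not counted |

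Subjects are lost from both rows, so the direction of any bias depends on which row loses the larger share.

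**Formula.** Let p be the PPV over all such biopsied subjects, c1 the chance that surgery is cancelled after a positive biopsy, and c0 the chance after a negative one. PPV is taken over PET-positive subjects, as the formula in SAP 5.5.7 requires. Then

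observed PPV = p·c1 / [p·c1 + (1 − p)·c0].

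With p = 0.5, c1 = 0.8 and c0 = 0.2: 0.40 / (0.40 + 0.10) = 0.80.

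**Range.** All values of p, c1 and c0 are assumptions.

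| c1 | c0 | p = 0.5 | p = 0.7 | p = 0.9 |
|---|---|---|---|---|
| 0.7 | 0.7 | 0.500 | 0.700 | 0.900 |
| 1 | 0.75 | 0.571 | 0.757 | 0.923 |
| 1 | 0.5 | 0.667 | 0.824 | 0.947 |
| 0.75 | 0.25 | 0.750 | 0.875 | 0.964 |
| 0.8 | 0.2 | 0.800 | 0.903 | 0.973 |
| 0.5 | 0.75 | 0.400 | 0.609 | 0.857 |

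Equal rates leave p unchanged, c1 > c0 raises the estimate, and c1 < c0 lowers it. In absolute terms the distortion shrinks as p approaches 1.

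**Effect on the comparison with 0.5.** This is the probability, by exact binomial enumeration, that the Agresti-Coull lower limit exceeds 0.5 when p really is 0.5, for an assumed 20 or 30 biopsied subjects:

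| c1 | c0 | 20 biopsied | 30 biopsied |
|---|---|---|---|
| 1 | 1 | 0.0207 | 0.0214 |
| 0.7 | 0.7 | 0.0230 | 0.0222 |
| 1 | 0.75 | 0.0845 | 0.0987 |
| 1 | 0.5 | 0.2468 | 0.3363 |
| 1 | 0.25 | 0.5759 | 0.7773 |

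**Worked count (assumed).** Twenty subjects are biopsied, 12 positive and 8 negative. Six of the 8 negatives go on to surgery; none of the positives do. Under the SAP rule the PPV is 12/14 = 0.857 (0.588 to 0.972), which excludes 0.5. Counting every biopsy gives 12/20 = 0.600 (0.386 to 0.782), which includes it.

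**Scope.** These figures concern the Cohort A component. SAP 3.2.3, item 6, pools both cohorts, and the two Cohort B rows in 5.5.7.4 do not carry this biopsy-then-surgery filter, so the pooled figure would move less.

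**The case against.** A reader might infer that the PPV is inflated by construction. The documents do not support that. Only the exclusion is built in: positive biopsies followed by surgery are dropped too, and a negative biopsy without surgery stays in as a false positive. Nothing in either document says how a biopsy result affects the decision to operate. Higher cancellation after a positive result is the expected pattern, since a negative result removes a reason to change the plan, but that is a judgement.

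It is also tempting to say that the lost false positives appear in no analysis. SAP Table 4 lists Safety Set summaries of imaging, histology and procedures, which may include them. What is missing is an accuracy estimate.

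Nor is it established that Protocol 12.5.2.3 imposes the same filter. It excludes evaluable subjects, not operated ones. Protocol 8.2 says that a subject who reports an alternate procedure for prostate cancer before surgery should be discontinued. If such a man were treated as non-evaluable, he could qualify under the protocol's rule. His coding is unclear.

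The sponsor can fairly say that SAP section 10 declares the move to a changed-procedure PPV, and that SAP 3.2.3 agrees with it. That answers any charge of an undisclosed change. But objective 5 in SAP 3.1.3 was left as it was, and section 10 does not mention the selection. The sponsor can also say that the plan changes on the scan, before any biopsy. SAP 4.2 does describe it that way, yet the set is coded on surgery not having been performed, not on a decision recorded at the scan.

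Finally, SAP 4.2 expects few such subjects and the endpoint is exploratory. Both points stand and limit the priority, although with few subjects a handful of lost negatives moves the estimate a good deal.

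**Conclusion.** The point holds as a selection problem with a likely but unquantified upward bias. The Cohort A component conditions on a decision that can come after the result being estimated, and the endpoint as coded does not answer objective 5 as still worded. At a true PPV of 0.5, the assumed cancellation patterns give observed values from 0.40 (reverse pattern) through 0.50 (equal rates) to 0.80 (0.8 versus 0.2). None of these rates is in the documents, and Figure 1, which the SAP cites for the definition of a change, was not available for this check. The primary and secondary results are unaffected. Priority: minor.

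**What to change.** 1. Keep the declared changed-procedure PPV in SAP 5.5.7.4 and 7.8, and describe it as selected on a decision that may follow the biopsy.
2. Add a PPV in all dosed subjects of either cohort who have location-matched histology from any alternate or additional procedure at a PET-positive site outside the planned template or biopsy site, whether or not the planned procedure followed. Use this one for objective 5.
3. Reconcile Protocol 8.2 with Protocol 10.3 and SAP 5.5.7.4 on how a subject who is biopsied and then operated on is coded.
4. Confirm that the eCRF captures that biopsy. Protocol 10.3 plainly covers it. For Cohort A, however, Protocol 10.5 speaks of subjects who forgo surgery, Table 3 footnote 6 of subjects whose planned procedure changes, and the SAP criterion pairs the unscheduled-biopsy field with surgery not performed.

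The cost is SAP wording and a little more analysis, with no new procedures, provided the data are captured as Protocol 10.3 says. The added PPV will probably be lower. Only lesions that someone chose to biopsy are verified under either version, so partial verification remains a limitation to state.

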#### 5.5.8. Lesions Per Subject

The number of lesions detected on imaging categorized as bone, lymph nodes, soft tissue, and the prostate gland will be determined by each of the central imaging core lab independent readers. The sum of lesions per subject per tissue type and overall will be computed for each subject based on each reader's lesion count. This will be calculated from the F-DCFPyL PET/CT scan results as well as the conventional imaging results.

Bone	Soft Tissue	Lymph nodes	Prostate Gland
BN Skull	ST Brain	LN Cervical	ST Prostate Gland Left
BN Thorax	ST Neck	LN Supraclavicular	ST Prostate Gland Right
BN Spine	ST Lungs	LN Axillary	
BN Pelvis	ST Esophageal	LN Mediastinal	
BN Extremities	ST Liver	LN Hilar	
	ST Gall Bladder	LN Mesenteric	
	ST Spleen	LN Elbow	
	ST Pancreas	LN Popliteal	
	ST Adrenal	LN Peri-aortic/para-aortic	
	ST Kidney	LN Other, Non-Pelvic	
	ST Bladder	PLN Template Right	
	ST Prostate Bed	PLN Template Left	
	ST Seminal Vesicle	PLN Pre-Sacral	
	ST Skin	PLN Other, Pelvic	
	ST Muscle		
	ST Other		

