3.3. Targeting PSMA for Prostate Cancer Detection

Prostate-specific membrane antigen (PSMA), also known as folate hydrolase I (FOLH1) or glutamate carboxypeptidase II (GCPII), is a trans-membrane, 750-amino acid type II glycoprotein primarily expressed in normal human prostate epithelium at very low levels, if at all, but is upregulated in prostate cancer, including metastatic disease. PSMA is a unique exopeptidase with reactivity toward poly-gamma-glutamated folates that is capable of sequentially removing the poly-gamma-glutamyl termini.^{29,30} Since PSMA is expressed by virtually all prostate cancers and its expression is further increased in poorly differentiated, metastatic and hormone-refractory prostate carcinomas, it is a very attractive target for developing agents for the diagnosis and staging of this disease.^{31,32,33} In addition to high expression in malignant prostatic tissue and being directly related to tumor aggressiveness,³⁴ PSMA has also been detected in renal proximal tubules, in cells of the intestinal brush border membrane, in rare cells in the colonic crypts, in brain, salivary glands,^{23,31,35,36} and in the neovasculature of nonprostatic solid carcinomas (e.g., renal cell, breast, colon, pancreas, melanoma, and lung carcinoma).²¹

A radiolabeled anti-PSMA monoclonal antibody (mAb) 7E11, marketed as Indium 111 ProstaScint® (capromab pendetide) is currently being used to detect prostate cancer nodal metastasis and recurrence. ProstaScint was first approved for marketing by the FDA in 1996, and while still available today, it is rarely used in practice due to a number of logistical and clinical limitations. Furthermore, ProstaScint targets the intracellular domain of PSMA and is therefore thought to bind mostly necrotic portions of the prostate tumor.³²

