7. SELECTION AND WITHDRAWAL OF SUBJECTS

7.1. Subject Inclusion Criteria

Subjects must meet all of the following inclusion criteria:

All Cohorts:

- 1. Adults ≥ 18 years of age.
- 2. Subjects provide signed informed consent and confirm that they are able and willing to comply with all protocol requirements.
- 3. Histologically confirmed adenocarcinoma of the prostate.

Cohort A Only:

- 4. At least high risk prostate cancer defined by NCCN Guidelines Version 3.2016 (clinical stage \geq T3a or PSA >20 ng/mL or Gleason score \geq 8).⁴⁷
- 5. Scheduled or will be scheduled to undergo radical prostatectomy with PLND.

Cohort B Only:

- 6. Radiologic evidence of local recurrence or new or progressive metastatic disease demonstrated on anatomical imaging (CT, MRI, or ultrasound), whole-body bone scan (^{99m}Tc-MDP or Na¹⁸F) within 4 weeks of Day 1.
- 7. If prior treatment with radiation or ablative therapy, evidence of recurrence outside the confines of prior treated site(s).
- 8. Scheduled or will be scheduled for percutaneous biopsy of at least one amenable lesion.

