10. ASSESSMENT OF EFFICACY

10.1. Image Acquisition

10.1.1. ¹⁸F-DCFPyL PET/CT (all cohorts)

¹⁸F-DCFPyL PET imaging will be performed on local PET/CT scanners with CT for correction of physical effects (e.g., attenuation, scatter) and anatomic localization.

At 1-2 hours post ¹⁸F-DCFPyL injection, the subject will be asked to void, and a whole body CT and PET scan will be acquired from the mid-thigh through the vertex of the skull. Parameters for PET/CT scanning can be found in the Imaging Manual.

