10.1.3. CT or MRI (all cohorts)

A contrast-enhanced CT of the chest, abdomen and pelvis (or non-contrast CT chest with Gadolinium-enhanced MRI of the abdomen and pelvis for subjects who have a medical contraindication to iodinated contrast) will be obtained at Screening if not already obtained within 6 weeks (Cohort A) or 4 weeks (Cohort B) prior to study drug injection. If CT is conducted at Screening, IV iodinated contrast medium cannot be administered within 24 hours of study drug injection. High density oral contrast medium (oral water contrast is acceptable) cannot be administered within 5 days prior to study drug injection. Copies of baseline CT or MR images will be submitted to the independent central imaging core lab per instruction in the Imaging Manual for assessment.

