#### 7.7.3. Detection Rates for Lesion Counts in both Cohorts Combined

For subjects in Cohort A and B combined, the sum of the lesions per tissue type and overall per subject will be summarized showing the N, mean, median, standard deviation, minimum and maximum values for each central imaging core lab reader including the reader of conventional scans. F-DCFPyL images and conventional images will be summarized separately and the mean of each reader's results from F-DCFPyL PET/CT will be compared to conventional imaging using a one-way repeated measures ANOVA. If the assumptions are not met for this test (see Section 7.2), then a Friedman's test will be performed to determine if there is a difference between any of the groups. If significant is determined from either the ANOVA or the Friedman's test, then a Dunnett's test will be performed to show where the difference exists between each reviewer and the conventional scan. A p-value and 95% confidence interval for the difference in means will be presented for each F-DCFPyL PET/CT reviewer versus conventional imaging. This analysis will be performed on the Evaluable Set.

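### The PET-versus-conventional lesion comparison sums regions that the two work-ups do not both image, so part of any difference can reflect coverage rather than detection

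*SAP*

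**What the plan says.** The comparison of detection rates for lesion counts, overall and by location, is a secondary efficacy endpoint for Cohorts A and B combined (Protocol 5.2, SAP 3.2.2). Five passages define it.

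- **PET field.** Protocol 10.1.1: a whole-body "CT and PET scan will be acquired from the mid-thigh through the vertex of the skull".
- **Conventional cross-sectional field.** Protocol 10.1.3 requires "A contrast-enhanced CT of the chest, abdomen and pelvis" or, where iodinated contrast is contraindicated, "non-contrast CT chest with Gadolinium-enhanced MRI of the abdomen and pelvis".
- **Bone scan.** Protocol 10.1.2 requires one but states no field. Cohort B criterion 6 in Protocol 7.1 calls it whole-body.
- **Count.** SAP 5.5.8: "The sum of lesions per subject per tissue type and overall will be computed for each subject". The same rule applies to PET and to conventional imaging. The region list includes ST Brain, ST Neck, LN Cervical, LN Popliteal and BN Extremities.
- **Test.** SAP 7.7.3: each PET reader's mean count "will be compared to conventional imaging using a one-way repeated measures ANOVA", or Friedman's test if assumptions fail. A Dunnett follow-up and a p-value and 95% confidence interval are planned for each reader against conventional imaging.

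Neither document limits the compared sums to a shared field or plans a common-field sensitivity analysis. Neither says whether a region that was not imaged counts as zero or as missing; SAP 5.6.1 says only that nothing is imputed.

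**The concern.** A count comparison measures relative detection only where both modalities had the chance to see a lesion. Where only one looked, its count enters the difference with nothing to set against it, and the p-value cannot tell that apart from better detection. Secondary objective 3 concerns detection rates by lesion location, so a result from SAP 7.7.3 would naturally be read as one modality finding more disease than the other.

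The plan applies the matching principle elsewhere. For the primary endpoint, SAP 5.5.7.1 lets an imaging result count as positive only if tissue was removed from the corresponding area, and Protocol 12.3.1 leaves out PET nodes in areas not resected. SAP 5.5.8 has no counterpart. The lesion counts also have no histology behind them, and SAP 7.7 runs the secondary analyses whatever the primary result.

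**Working it through.** **Step 1: set the fields against the region list.** The plan gives no lesion rate, SD or power for this endpoint, so there is no planned figure to reproduce.

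| SAP 5.5.8 label | PET/CT, mid-thigh to vertex | Required CT or CT/MRI | Bone scan |
|---|---|---|---|
| ST Brain, ST Neck | inside | outside | not applicable |
| LN Cervical | inside | outside | not applicable |
| BN Extremities, below mid-thigh | outside | outside | inside if whole-body |
| BN Extremities, proximal femur to mid-thigh | inside | not the relevant scan | inside if whole-body |
| LN Popliteal | outside | outside | not applicable |

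The labels that can favour PET through coverage are 2 of the 16 soft-tissue labels and 1 of the 14 nodal labels. BN Skull and the cervical part of BN Spine lie within a whole-body bone scan, so they do not favour PET in this way. Bone below mid-thigh can favour conventional imaging.

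**Step 2: does the unstated coding matter?** There are three possibilities for a region that was not imaged.

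- Coded zero: the conventional sum gains nothing there and the PET sum can.
- Skipped in the sum: the arithmetic is the same as zero.
- Treated as making the whole sum missing: every subject whose conventional scan stopped at the required field drops out.

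None of these gives a like-for-like comparison. That needs the region removed from both sums for the subject.

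**Step 3: how large could it be? Illustration on assumptions only.** Let δ be the mean number of out-of-field lesions per subject added to PET (Poisson) and SD the standard deviation of the in-field paired difference, whose mean is zero. One PET reader is tested against conventional imaging by a paired t-test at two-sided 0.05 (the level in SAP 7.1), as a stand-in for the planned ANOVA and Dunnett test. Assumed N = 339: the 236 evaluable in Cohort A, plus about 103 in Cohort B if the 10% loss is also applied there (115 × 0.9 = 103.5).

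Approximate chance of significance = Φ(λ − 1.96) + Φ(−λ − 1.96), with λ = √N × δ / √(SD² + δ).

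For δ = 0.10 and SD = 1.0: λ = 18.41 × 0.10 / √1.10 = 1.76, so the chance is about Φ(−0.20) = 0.42. Simulation with 4,000 repetitions gave 0.427. Simulated results for N = 339:

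| SD | δ = 0 | 0.02 | 0.05 | 0.10 | 0.20 |
|---|---|---|---|---|---|
| 0.5 | 5% | 11% | 40% | 88% | 100% |
| 1.0 | 5% | 7% | 14% | 43% | 92% |
| 2.0 | 5% | 5% | 7% | 15% | 44% |

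N of 300 and 377 gave similar figures. The table models only the part that favours PET; bone lesions below mid-thigh would offset some of it in the overall count. It does not carry over directly to Friedman's test, which uses ranks.

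**The case against.** The strongest reply is that comparing each work-up as performed, coverage included, is a legitimate question, and that this is an unpowered secondary endpoint outside the multiplicity scheme in SAP 7.5. That stands. It is why the all-region counts should be kept. It does not make them evidence about detection in tissue that both modalities imaged.

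Several stronger readings are tempting, and the documents do not support them.

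- **Head and neck findings can only add to PET.** Protocol 10.1.3 states a required field, not a maximum. Standard-of-care scans are accepted, and the bone scan may be an NaF PET/CT, so some conventional imaging may reach the neck or head.
- **Conventional imaging has a built-in zero there.** The coding is not stated. Reading rules sit in the Imaging Manual and Imaging Review Charter, which were not available.
- **The overall comparison leans to PET.** Bone below mid-thigh may pull the other way, so the net direction is unknown. That pull is itself uncertain, because only criterion 6 calls the bone scan whole-body.
- **Every label outside chest, abdomen and pelvis biases the result.** LN Popliteal is in neither field, and PET coverage of LN Elbow is unstated. Label counts are not lesion rates in any case.
- **Normal PSMA expression inflates the PET count.** Protocol 3.3 does report PSMA "in brain, salivary glands". But it also names kidney and intestine, which both modalities image. That is a question of false positives, not of coverage, and nothing says readers count physiologic uptake as lesions.

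One more moderating fact: subjects whose planned procedure changed after PET leave the secondary endpoints (SAP 4.1 and 4.2), which may remove some with distant PET findings.

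**Conclusion.** The point holds in a limited form. SAP 5.5.8 and 7.7.3 test counts summed over regions that the required scans do not share, so part of any soft-tissue, nodal or overall difference can come from coverage. The affected labels are ST Brain, ST Neck and LN Cervical on one side and, if the bone scan is whole-body, bone below mid-thigh on the other.

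The size cannot be determined from the documents. On the assumptions shown it runs from negligible (5% to 11% significant results at 0.02 extra lesions per subject) to dominant (44% to 100% at 0.20), depending on the SD. The net direction for the overall count is likewise undetermined. The conclusion rests on the required fields applying to most subjects and on no shared-field rule existing in the unseen imaging documents.

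The co-primary endpoints use pelvic nodes only and are unaffected. This is a worthwhile, inexpensive improvement to a secondary endpoint, not a threat to the trial's main result.

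**What to change.** In SAP 5.5.8 and 7.7.3:

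1. Add a PET-versus-conventional comparison limited to regions imaged by both modalities, and base any claim about relative detection on it.
2. For soft tissue, nodes and overall, exclude ST Brain, ST Neck and LN Cervical from both sums unless the subject's conventional scan covered them.
3. For bone, exclude lesions below mid-thigh where the location is recorded. Otherwise show bone with and without BN Extremities. Deleting that label outright would also discard proximal femur, which the PET field includes and a whole-body bone scan would too.
4. Code an unimaged region as not evaluable rather than zero.
5. Keep the all-region counts as a description of each work-up as performed.
6. Show both by cohort as well as combined. Criterion 6 admits Cohort B on "Radiologic evidence of local recurrence or new or progressive metastatic disease demonstrated on anatomical imaging" or a bone scan, while Cohort A has no such selection. SAP 5.1 already promises efficacy tables by cohort.

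The cost is SAP wording and some extra output. Counts by region are already recorded, and the conventional images are already sent to the core lab, which could confirm coverage where it exceeds the required field. The downside is that a few real lesions outside the shared field leave the tested comparison; list them by modality instead. Catch-all labels such as ST Other and LN Other, Non-Pelvic may still hold some out-of-field lesions unless their location is recorded.
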